#### Methods:

For the main analysis model, we used PROC GENMOD to fit models based on generalized estimating equations with a logit link and an independence correlation structure using the attending physician as the clustering unit with month and site as covariates. In sensitivity analyses, the main model was estimated by also adjusting for patient characteristics including age, sex, race,...,..,etc.

To obtain the adjusted difference in the percentage of patients receiving daily IGRT imaging between intervention and non-intervention groups and 95% confidence intervals (CIs), we used the bootstrap method, resampling patients 1000 times. Resampling of patients was by physician to maintain clustering at the physician level. All analyses were conducted in SAS version 9.4.

7

**Commented [SS7]:** CR: Note: It's possible we might use a different correlation structure. We can modify what goes in the list of the covariates for the sensitivity model.

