# 5.3 Target population

The study will include a total of ~29 subjects (UPHS radiation oncologists) and 5 sites across the UPHS network (Perelman Center for Advanced Medicine, Pennsylvania Hospital, Chestnut Hill Hospital, Doylestown Hospital, and Valley Forge) that treat about 800 palliative patients a year. The University of Pennsylvania Radiation Oncology network (both PCAM and satellites) will be the only site of this study.

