# 2. Unadjusted Analysis

- a. Daily IGRT
  - i. Calculate daily IGRT use during pre-intervention period (2/10/16-2/9/17)
    1. Display graphically by month and cohort (PCAM vs. satellites)
  - ii. Calculate daily IGRT use at PCAM and satellites after intervention implemented (2/10/17-10/10/17)
    - 1. Display graphically by month and cohort (PCAM vs. satellite)
    - 2. Indicate on graph when intervention occurred at PCAM (2/10/17) and satellites (6/10/17)
  - iii. Conduct statistical analysis of change in daily IGRT pre and post intervention with 95% CI and p values
    - 1. Change in daily IGRT use from baseline pre-intervention period to intervention periods in both the control and intervention arms
      - Intervention group: Pre-intervention period (2/10/16-2/9/17) use of daily IGRT vs. Post-intervention period (3/10-17-10/10/17) use of daily IGRT
      - Control group: Pre-intervention period (2/10/16-6/9/17) use of daily IGRT vs. Post-intervention period (7/10-17-10/10/17) use of daily IGRT
    - Change in daily IGRT use during first intervention period (3/10/17-6/9/17) between usual care group (control) and intervention arms

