#### 3. Adjusted Analysis

- a. Primary model
  - i. Adjust for:
    - 1. Intervention
    - 2. Attending (clustering at level of attending)
    - 3. Location (PCAM vs. Satellites)
    - 4. Time

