#### b. Primary model + relevant patient level factors

- 1. Intervention
  - 2. Attending (clustering at level of attending)
  - 3. Location
  - 4. Time?
  - 5. Age
  - 6. ECOG
  - 7. Prior radiation
  - 8. Insurance type (Commercial, Medicare , Medicaid, Uninsured, Unknown)
  - 9. Total number of fractions per course
- c. Sensitivity model
  - i. Covariates:
    - 1. Cohort (intervention vs. control arms)
    - 2. Age
    - 3. Sex
    - 4. Race
    - 5. ECOG
    - 6. Insurance type (Commercial, Medicare , Medicaid, Uninsured, Unknown)
    - 7. Target type (Brain, bone, soft tissue, multiple sites, other)
    - 8. Prior radiation (course 1 vs. not course 1)
    - 9. Total number of fractions per course

Commented [SS6]: Time defined as days from intervention?

- 10. Dose per fraction
- 11. Attending
- 12. Time of day
- 13. Location (PCAM vs. satellite)
- d. Assess missing data
- e. Unadjusted and adjusted analyses for covariates in relation to primary outcome (daily IGRT use)

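### The main GEE clusters on about 29 attendings with no small-sample method: an uncorrected Wald z-test would reject too often, and a percentile cluster bootstrap would cover somewhat less than 95%

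*SAP*

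**What the plan says.** The SAP's Methods section describes the main analysis as "models based on generalized estimating equations with a logit link and an independence correlation structure using the attending physician as the clustering unit". The covariates are month and site. It then takes the adjusted difference in the percentage of patients with daily imaging, and its 95% CI, from 1,000 bootstrap resamples: "Resampling of patients was by physician to maintain clustering at the physician level". The interval type (percentile, SE-based or other) is not given.

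The number of clusters comes from protocol section 5.3: "The study will include a total of ~29 subjects (UPHS radiation oncologists) and 5 sites across the UPHS network". Neither document splits the physicians between PCAM and the satellites.

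P values are requested only under SAP section 2, Unadjusted Analysis: "Conduct statistical analysis of change in daily IGRT pre and post intervention with 95% CI and p values". No test is named there either. SAP section 3, Adjusted Analysis, and the Methods section name no test of the intervention term, no degrees of freedom and no small-sample variance. Alpha and sidedness are also not stated.

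Three parts of the model are unsettled:
- **Time.** It is month in Methods and plain time in the primary model. A margin comment asks whether it should be "Time defined as days from intervention".
- **Working correlation.** A margin comment says "It's possible we might use a different correlation structure".
- **Model.** Protocol section 9 specifies a mixed effects logistic regression with physician random effects instead, also without a small-sample method.

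**The concern.** Under an independence structure the working model makes no allowance for clustering, so all of it comes from the empirical sandwich variance. With few clusters that variance is biased low, because the fitted model has already been pulled towards each physician's own data. Referring the estimate to a normal distribution adds an error in the same direction, since it treats the estimated SE as known.

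Twenty-nine clusters are few, and the effective number may be smaller. In the first intervention period the satellites are the only controls, and the number of satellite attendings is not reported.

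At stake is whether the nominal 5% and 95% mean what they say. A default order set that changes nothing could be declared to have changed imaging more than one time in twenty, and the reported interval could be too narrow. A percentile cluster bootstrap does not automatically escape this.

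**Working it through.** **The plan's own figures.** The plan gives no type I error or coverage figure to reproduce. Its nearest figure is the 89% power for a 0.2 reduction (protocol section 9). Treating patients as independent over two months gives 623 x 2/12 = 103.8 PCAM and 202 x 2/12 = 33.7 satellite courses. With 0.593 against 0.793, the pooled rate is 0.642. The null SE is sqrt(0.642 x 0.358 x (1/103.8 + 1/33.7)) = 0.095. The alternative SE is sqrt(0.593 x 0.407/103.8 + 0.793 x 0.207/33.7) = 0.0848. Power is Phi((0.2 - 1.96 x 0.095)/0.0848) = 0.56. The protocol gives no intraclass correlation or formula, so 89% cannot be checked. Nothing below depends on it.

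**Estimator.** With U_i = X_i'(y_i - mu_i) for physician i and A = sum of X_i'W_iX_i, the sandwich is V = A^-1 (sum of U_iU_i') A^-1. The Wald z-test rejects when |b|/sqrt(V_bb) > 1.96. Mancl-DeRouen replaces each residual r_i by (I - H_ii)^-1 r_i and refers the ratio to t on G - 2 degrees of freedom, here 29 - 2 = 27.

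**Inputs from the documents.**
- Calendar (SAP): 12 pre-intervention months, 3 months with PCAM only, 3 months with both groups; roll-out months dropped.
- Volume (protocol Table 2): 623 PCAM courses a year and 56 + 39 + 55 + 52 = 202 satellite courses.
- Baseline (Table 2): PCAM 81.4%; satellites (56 x 0.589 + 39 x 0.795 + 55 x 0.764 + 52 x 0.808)/202 = 148.0/202 = 73.3%.

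**Assumed, because the documents are silent.** Physician splits from 15/14 to 23/6; unequal caseloads (Dirichlet(2) shares); physician SD 1.0 on the logit scale; physician-by-period SD 0, 0.5 or 0.8. Sensitivity cells used 60% volume, equal caseloads or physician SD 0.5. There were 2,000 null data sets per cell; at 5% the Monte Carlo error is 1.96 x sqrt(0.05 x 0.95/2000) = 1.0 point, rising to about 1.5 points at the highest rates.

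**Wald z type I error (%), by physician-by-period SD 0 / 0.5 / 0.8.**

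| PCAM/satellite physicians | Month as categories | Linear month |
|---|---|---|
| 15/14 | 8.3 / 9.3 / 10.5 | 7.2 / 8.6 / 8.8 |
| 17/12 | 8.7 / 10.2 / 9.9 | 8.4 / 9.3 / 7.2 |
| 20/9 | 10.4 / 10.2 / 11.3 | 7.1 / 7.6 / 8.6 |
| 23/6 | 13.2 / 13.8 / 13.6 | 8.7 / 8.5 / 8.6 |

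**Range over all 30 cells per form of month (%), sensitivity cells included.**

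| Test | Month as categories | Linear month |
|---|---|---|
| Wald z | 7.7-13.9 (7.7-11.3 without 23/6) | 6.2-9.3 |
| Same SE, t(G-2) | 6.4-12.6 | 5.2-7.7 |
| Mancl-DeRouen, t(G-2) | 3.6-6.7 | 3.8-6.3 |
| GEE score test | 2.9-5.9 | 4.0-6.0 |

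A separate simulation with other variances (physician SD 0.5-0.8) and caseloads agreed: Wald z 6.8-12.0%, Mancl-DeRouen 4.0-5.4%, score test 3.6-5.8%. A further one at physician-by-period SD 0.5 over three splits gave Wald z 6.9-8.5% (linear) and 8.6-11.8% (categories), against 4.0-5.6% for Mancl-DeRouen.

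**Coverage of a 95% percentile bootstrap interval under no effect.**
- Whole physicians, unstratified: 91.5-92.4% (categories) and 91.9-93.2% (linear) with 1,000 data sets and 500 resamples. The separate simulation gave 91.0-94.0%; its one run at the planned 1,000 resamples gave 93.7%.
- Patients within fixed physicians: 92.5-94.0% at physician-by-period SD 0. At SD 0.5 it was 86.8-88.0% (categories) and 89.2-91.1% (linear); the separate simulation fell to 82.2% at SD 0.8.

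**Other intervals.** One 20/9 configuration (whole physicians, 400 resamples, 1,000 data sets) gave, linear / categories: percentile 92.7% / 92.5%; estimate +/- 1.96 bootstrap SE 92.6% / 94.1%; bootstrap SE with t(27) 94.0% / 95.4%. The delta-method interval from Mancl-DeRouen with t(G-2) covered 94.4-95.6% / 93.5-95.5%.

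**The case against.** The strongest reply is that the SAP never says it will use a Wald z-test. Its stated inferential output is the bootstrap interval, and the score test, which it could equally use, stays close to 5%. That is fair, and it is why the figures here are conditional. It does not remove the point, because nothing in either document steers the analyst away from the uncorrected choice.

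Four stronger readings are tempting, and the documents do not support them.
- **The planned bootstrap CI necessarily falls short.** No interval type is named. The shortfall shown is for the percentile interval, and a whole-physician bootstrap SE with t was near 95%. The SAP's wording most naturally means drawing whole physicians, so the much lower within-physician coverage is a risk of ambiguity and not the plan as written.
- **The bootstrap errs up to 11% of the time.** That figure needs resampling stratified by group (coverage down to 88.9%), which the SAP does not describe. The unstratified version in the same simulation excludes zero 6.8-8.5% of the time (100 - 93.2 to 100 - 91.5).
- **Type I error is 14%.** This needs month as categories and an assumed 23/6 split together.
- **A small-sample correction secures 5%.** The coin flip assigns two groups, and protocol section 9 acknowledges that. When an assumed group-by-period SD of 0.2 logit was added, Mancl-DeRouen with t(27) rejected a true null 10.4% (linear) and 8.9% (categories) of the time. At SD 0.3 it was 13.5% and 13.9%.

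The volumes are also somewhat high: the 831 courses behind Table 2 match the Table 1 total, which includes 21 SBRT courses that the protocol excludes. The 60% volume cells lie within the ranges given.

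**Conclusion.** The point holds as a conditional one of moderate size. The omission itself is certain: an independence GEE on about 29 clusters, with nothing in either document to handle the small number. A t reference alone on the uncorrected SE is not enough when month is categorical; a corrected sandwich or the score test is.

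The consequence depends on choices left open. With the uncorrected z-test the error is roughly 6-9% or 8-11%, according to the form of month. With an unstratified whole-physician percentile interval, coverage is a few points short of 95%, and some single runs are within simulation error of it. These sizes rest on the assumed splits, caseloads and variances, on a two-sided 5% level, and on the SAP's GEE rather than the protocol's mixed model. A different working correlation or a continuous time term would change them. The direction was the same in every simulation of the z-test.

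**What to change.** In the SAP's Methods section:

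1. Fix the form of month (categories or linear), the working correlation, and alpha and sidedness. Reconcile the GEE with the protocol's mixed effects model.
2. Base the p value for the intervention term on a Mancl-DeRouen-corrected sandwich with t on the number of physicians minus 2, or on the GEE score test. The corrected sandwich lets the p value and the CI share one variance. The score test was conservative in some 23/6 cells.
3. Take the CI of the adjusted difference from the corrected variance by the delta method. Alternatively, keep the bootstrap, draw whole physicians with all their courses, and use the bootstrap SE with a t reference instead of a percentile interval.
4. Report the number of physicians in each group.
5. State the limit: this corrects for few physicians only. Any PCAM/satellite-by-period variation stays outside a physician-level correction.

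The cost is a few sentences and some programming. The corrected interval is modestly wider: a median 10-15% against a percentile interval from a group-stratified bootstrap, the only comparison made. Nominal power for the 0.2 reduction is lower than for the inflated z-test. With linear month the loss is small: 0.89-0.95 (Mancl-DeRouen) and 0.92-0.96 (score) against 0.93-0.97. With month as categories it is larger: 0.45-0.60 and 0.42-0.66 against 0.64-0.77. The form of month and the test should therefore be decided together.
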